The clinical trials that compared the NOACs to warfarin did not specifically study ARN and did not repeat creatinine and urinalysis testing in the first two to three months of therapy to establish possible ARN diagnosis [15-20]. In most of these studies, only baseline creatinine and creatinine levels 6 to 12 months later were analyzed, hence it is possible that ARN was under-diagnosed as most cases of ARN are detected in the first eight weeks of therapy. Our study aims to accurately capture ARN cases by making these measurements monthly in the first three months of starting the anticoagulant.

This study is pivotal because it will for the first time, define the incidence of ARN in patients on rivaroxaban or apixaban therapy. If we find that ARN incidence in patients started on rivaroxaban or apixaban is less than that seen with warfarin, this can help support evidence that this NOAC is safer for the kidneys compared to warfarin and this data can enable us make evidence based decisions regarding the continued use of the medication to help our patients. If on the other hand we find that the medication leads to ARN, then we will be contributing important post-marketing surveillance data that can also help us make safety decisions about the use of the medication in the future.

INNOVATION

Previous studies on ARN have utilized retrospective study designs which have many epidemiological pitfalls including the cause versus effect bias and the inability to ascertain relative risk [1]. Our study is unique because we intend to utilize a prospective epidemiological design to study this renal complication, a first in the study of ARN. This is important because ARN is a diagnosis of exclusion and hence a prospective study is able to more accurately define cases of the condition compared to the assumptions that are made in retrospective studies where further work up cannot be done in retrospect.

This will be the first epidemiological study focused on ARN in a NOAC. Even though NOACs are new, they are becoming ubiquitous and a mainstay in clinical practice and not just an alternative to warfarin. For example, the recent CHEST guidelines recommend them as first line therapy in the treatment of venous thromboembolism [8]. Hence it will be important to clearly delineate their effects on the kidneys.

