- Montgomery campus
- Other: please specify -

b. Indicate if human research will be conducted at external location(s) overseen by the AEHN investigator (e.g. private physician office, collaborating hospital/university)

- Yes (Complete Appendix B: External Site Approvals on Application for Human Research)
- No

5) Resources available to conduct the Human Research:

a. Target population (e.g. Adult subjects with a diagnosis of Type II diabetes for greater than two years?": Elderly patients with CKD who have recently been started on Rivaroxaban or Apixaban

b. For prospective studies:

- i.) Total number of subjects planned to be enrolled in the study at AEHN site(s): 40
- ii) For multi-site projects, please indicate total number of subjects planned to be enrolled in the study at all sites: 0
- iii) Describe access to a population that would allow recruitment of the targeted number of subjects (*i.e. how many potential subjects do you have access to? What percentage of those potential subjects do you need to recruit?*) : We estimate that around 100 patients meeting our criteria are started on Apixaban or Rivaroxaban in a six-month period. We anticipate to recruit 40% (40) of them into the study

c. For retrospective studies:

- i.) Estimated number of charts to be reviewed: N/A
- ii.) Time period of interest for data being collected (*e.g. Subjects who had XX procedure between 6/1/00 and 6/1/05*): N/A

d. Describe the number and qualifications of the study team members, their experience in conducting research, their knowledge of the local study site(s), culture, and society:

Principal Investigator: [name] is a first year intern in Internal Medicine at Albert Einstein Medical Center. [name] completed her medical school training at the University of Jordan in Jordan where she graduated top of her class. She completed a graduate degree in Public Health at Thomas Jefferson University in Philadelphia and she is interested in population epidemiology and determinants of health. At Einstein, he has been very keen to work on research projects with collaboration with other colleagues on various projects

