Screening will be also be carried out by a query on the electronic medical record with a confidential report generated weekly by the Einstein's AECIS which will contain all rivaroxaban and apixaban prescriptions ordered by electronic scripts. Investigators and co-investigators will review the medical records of patients on the list to determine if they meet the inclusion criteria for the study.

Identified patients will be given a written description about the study and [name] (principal investigator) will be notified. All identified patients will have their medical records/chart reviewed by [name] to determine eligibility for the study. If appropriate, he will then contact them by phone and arrange a meeting to discuss the study protocol, answer any questions and complete the consent process

- ii. Describe the criteria that define who will be included or excluded in your final study sample:

Inclusion Criteria

- Age \geq 60 years
- GFR \leq 90 ml/L based on creatinine clearance
- Participant has been initiated on long term anticoagulation with rivaroxaban or apixaban for atrial fibrillation within four weeks of recruitment
- Participant is willing to comply with all aspects of the protocol, including adherence to medical therapy and follow-up visit
- Participant is willing to give written informed consent

Exclusion Criteria

- History of blood dyscrasias or active bleeding,
- History of hematuria
- Patients on dialysis

c. Study Timelines:

- i. Duration of an individual subject's participation in the study: 6 months
- ii. Time period anticipated to enroll all study subjects or to complete chart review: 4 months
- iii. Estimated overall study duration (*i.e. from initiation to completion of primary analyses*): 12 months

d. Study Endpoints:

- i. Describe the primary and secondary study endpoints (*i.e. the outcome(s) that the study is designed to evaluate*):

Primary endpoint - Incidence of ARN is the primary outcome of this study and this is based on a documentation of AKI (defined as an increase in baseline serum creatinine \geq 0.3 mg/dL), in the absence of any other obvious etiology for the AKI identified after a standard clinical evaluation and work up by the patient's primary care physician, cardiologist or nephrologist. This incidence will be expressed as a percentage.

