Secondary endpoint - Urinalysis measurements (particularly hematuria and proteinuria) will be analyzed for correlation with the incidence of ARN. Demographic variables including age and race will be analyzed in contingency tables using Fisher's exact test to ascertain if they are significant for the primary outcome.

- ii. Describe any primary or secondary safety endpoints (*e.g. any disease or symptom that would result in the withdrawal of that subject from the study*): Subjects will be censored from the study if anticoagulation is withdrawn for any clinical reason

e. Human Research Methods:

- i. Describe and explain the study design (*e.g. randomized, double-blind, placebo-controlled clinical trial or retrospective chart review*):

This is a prospective observational study designed to determine the incidence of ARN in 40 adult patients recently initiated on rivaroxaban or apixaban at Einstein Medical Center Philadelphia.

- ii. Describe all research activities involved in this protocol, including a study visit timeline if appropriate:

Baseline demographic data, past medical history, current medication list and baseline laboratory records (taken within the last three months) will be obtained from the patient's hospital chart and the electronic medical record. Serum creatinine and urinalysis measurements will then be repeated at monthly intervals for the first three months and then at the six-month mark. These laboratory tests will be drawn at Einstein's Klein building Suite 100 by a trained phlebotomist.

If AKI, defined as an increase in baseline serum creatinine ≥ 0.3 mg/dL from baseline, is noted in any study participant, the patient and his primary care physician or cardiologist will be notified both verbally and through a detailed letter. A standard clinical evaluation and work up will then be performed by the patient's primary care physician or cardiologist as part of the patient's usual care with referral to a nephrologist if necessary. The research team will then be notified of the result of this work up.

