[name] will create a "study participant list" that contains the names and birth dates of all study subjects and assigns them a unique three digit identification number. This list will be password encrypted and stored on the Einstein computer network. A separate encrypted "study database" will be constructed and baseline data, laboratory results and work up data will be aggregated into this database using the identification numbers. Following the completion of the study, the initial study participant list will be deleted. All data will be checked twice upon entering it into the database to ensure accuracy.

- iii. Identify which tests/procedures are being administered solely for research purposes and which are being conducted as part of standard of care (i.e. procedures that would be done even if the participant were not involved in research):

Serum creatinine and urinalysis measurements monitored in the first six months after starting anti-coagulation will be test done for research purposes.

If AKI, defined as an increase in baseline serum creatinine ≥ 0.3 mg/dL from baseline, is noted in any study participant, the patient and his primary care physician or cardiologist will be notified both verbally and through a detailed letter. A standard clinical evaluation and work up will then be performed by the patient's primary care physician or cardiologist as part of the patient's usual care with referral to a nephrologist if necessary.

- iv. Describe steps taken to lessen the probability or magnitude of risks associated with tests/procedures being done for research purposes only (*e.g. only appropriately trained personnel involved in procedures, extra tests being done for safety purposes*):

The tests proposed for the study subjects are serum creatinine assay and urinalysis. Obtaining a sample for urinalysis is not an invasive test and does not portend any major risk to participants. Serum creatinine assay will involve four blood draws during the course of the study. Blood draws involve using a needle to obtain blood from a peripheral vein. This procedure is a low risk procedure however, it may cause pain, bleeding or bruising. To minimize this risk, we will employ a phlebotomist who has been trained to do blood draws using standard techniques that cause the least discomfort.

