- v. Describe alternative treatments that are available to subjects if they choose not to participate in research: No new treatment is started in this study. Patients will be observed in on-going treatment that is started before the observation. Patients who do not participate will continue to receive standard clinical care.

- vi. Describe the source records that will be used to collect data: AECIS records for background demographic data. Laboratory results from the Einstein laboratory after serum creatinine and urinalysis are assayed.

- vii. Describe what data (variables) will be collected for this research: Baseline demographic data (age, sex, height, weight, race), past medical history, current medication list and baseline laboratory records (basic metabolic panel, serum creatinine, urinalysis) will be obtained from the patient's hospital chart and the electronic medical record. Serum creatinine and urinalysis measurements will then be repeated at monthly intervals for the first three months and then at the six-month mark.

- viii. Describe any plans to conduct audio or video recording of research participants during the conduct of the research. Specify whether recording is optional or not and how information on how recordings will be used and how long they will be retained is being shared with subject: N/A

f. Specimen Management:

- i. Will any type of specimen (e.g. blood or tissue) be collected for this study?
 Yes
 No, skip to section on Data Management
- ii. What information will be associated with the specimens collected for this study? Each sample will be labeled with the patient's unique identification number.
- iii. If specimens will be banked for future use, describe where and how the specimens will be stored:
 N/A

- iv. Specify how long specimens will be stored locally: N/A
- v. Specify who will have access to the specimens locally: N/A
- vi. Will specimens be sent out or received: No Yes
 - a. Who is responsible for receipt or transmission of the specimens? N/A
 - b. How will specimens be transported? N/A
 - c. Describe the procedures to release specimens, including: the process to request a release, approvals required for release, who can obtain specimens, and the data to be provided with specimens: N/A

g. Data Management

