- ii. Describe the procedures that will be followed when subjects withdraw from the research (or request that their data be withdrawn), including partial withdrawal from procedures with continued data collection: If a patient is censored from the study, all of their data will be removed from the study participant list and study database.

7) Risks to Subjects:

- a) List the reasonably foreseeable risks, discomforts, hazards or inconveniences to the subjects. For each indicate the probability, magnitude, and duration when possible (consider physical, psychological, social, legal and economic risks as well as risks related to confidentiality): This research has no additional risk above and beyond that of a blood draw and urine collection. Blood draws may rarely cause pain, bleeding and bruising. Blood draws for serum creatinine assay will be performed by a trained phlebotomist using standard techniques.
- b) If applicable, indicate which procedures may have risks to the subjects that are currently unforeseeable: None
- c) If applicable, indicate which procedures may have risks to an embryo or fetus should the subject or the subject's partner be or become pregnant: None
- d) Describe, if applicable, the process that will be followed if a subject or the subjects' partner becomes pregnant while participating in the study: None
- e) If applicable, describe risks to others who are not subjects: None

8) Potential Benefits to Subjects

- a) Describe the benefits that individual subjects may experience (include when possible the probability, magnitude and duration of the potential benefits) or indicate if there is no direct benefit: If a patient develops ARN, this study ensures that the condition will be detected and the patient will receive a comprehensive work up in standard care. The benefit to the patient is that they are receiving extra monitoring for this condition.

9) Medical care and compensation for injury (Required for Greater than Minimal Risk Studies Only):

- a) Describe any provisions for medical care and available compensation in the event of a research related injury: N/A
- b) Provide the contract language, if any, relevant to compensation for research-related injury: N/A

10) Cost to participants:

- a) Describe any actual or potential cost that subjects may incur through participation: There are no costs that the subject may incur.

11) Provisions to Protect the Privacy Interests of Subjects:

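### The primary endpoint has no stated route for AKI found between the four scheduled creatinine draws, so the six-month figure is incidence detected at scheduled draws and may understate six-month incidence

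*Protocol*

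**What the plan says.** **Schedule.** Study Design, e. Human Research Methods, items ii and vii: "Serum creatinine and urinalysis measurements will then be repeated at monthly intervals for the first three months and then at the six-month mark". Item iv confirms the number: "Serum creatinine assay will involve four blood draws during the course of the study". Study Timelines adds: "Duration of an individual subject's participation in the study: 6 months".

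**Sources.** Item vi of the same section names the source records: "AECIS records for background demographic data. Laboratory results from the Einstein laboratory after serum creatinine and urinalysis are assayed". Item vii lists the variables: baseline data from the chart and electronic record, then the scheduled creatinine and urinalysis measurements. No interim value is listed.

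**Endpoint.** Study Endpoints defines the primary outcome as documented AKI, a creatinine rise of at least 0.3 mg/dL from baseline, with no other evident cause after clinical work-up. It is reported as one percentage. On the baseline value, item ii says: "baseline laboratory records (taken within the last three months) will be obtained from the patient's hospital chart".

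**Rationale.** Section 3 says that anticoagulation-related nephropathy (ARN) mostly appears within about two months of starting treatment, and cites a proposed guideline for monthly checks early on. It says of most earlier trials that "only baseline creatinine and creatinine levels 6 to 12 months later were analyzed", and that ARN may have been under-diagnosed there.

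**Claims.** Section 8 says that "this study ensures that the condition will be detected" if a patient develops ARN. Data Management, item ii, reads a negative finding as a sign of very little risk among people in general.

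**The concern.** A creatinine rise that starts and settles between two draws is not seen by the study. The longest interval is the three months before the last draw. A clinician or hospital may well measure creatinine in that time, but the protocol does not say that such a value is collected or counted. The alert in Human Research Methods, item ii, runs from the study to the patient's physician. What comes back is the result of the work-up that follows. Nothing describes a report in the other direction when a clinician finds AKI first.

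Two things are at stake. The single six-month percentage combines three closely sampled months with three that have one draw at their end. And the planned reading of few or no cases, together with the statement in Section 8 that detection is assured, presumes near-complete capture, which four draws alone cannot give.

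**Working it through.** **Inputs from the protocol.** Sample size, Section 5b: "Total number of subjects planned to be enrolled in the study at AEHN site(s): 40". Draws at months 1, 2, 3 and 6. Warfarin reference 17-37% (Data Management, item ii). Most ARN detected within eight weeks (Section 3).

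**Assumptions of this check.** Draws on days 30, 61, 91 and 183, with day 0 the start of treatment and of observation. The rise stays above threshold for a fixed duration D, and onset is even within each stated period. An episode counts only if it is still present at the next draw. The protocol gives no duration, so a range is shown.

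**Step 1: the plan's own intervals.** Exact binomial limits with n = 40:
- 0 cases: upper limit 1 - 0.025^(1/40) = 8.8% (plan: 9%)
- 2 cases: 0.6% to 16.9% (plan: 0.6% to 17%)
- 10 cases: 12.7% to 41.2% (plan: 13% to 41%)

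They reproduce. They describe detected incidence.

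**Step 2: capture within a gap = min(1, D/gap).**
- Months 3-6, gap 183 - 91 = 92 days: 14/92 = 15%; 30/92 = 33%; 60/92 = 65%; 90/92 = 98%.
- Months 0-3, gaps of 30, 31 and 30 days: (3 x 14)/91 = 46%; (3 x 21)/91 = 69%; (3 x 30)/91 = 99%.

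**Step 3: weighting by time of onset.** Capture by the four draws:

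| Rise lasts | All onsets in first 8 weeks | 80% in first 8 weeks, rest even to month 6 | Even over 6 months |
|---|---|---|---|
| 14 days | 41% | 38% | 31% |
| 21 days | 66% | 60% | 46% |
| 30 days | 98% | 89% | 66% |
| 60 days | 100% | 95% | 83% |

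Middle column, 14 days: the first 56 days give (14 + 9)/56 = 41.1%, the other 127 days give (5 + 14 + 14)/127 = 26.0%, and 0.8 x 41.1 + 0.2 x 26.0 = 38%. For 30 days: 55/56 = 98.2%, 65/127 = 51.2%, and 0.8 x 98.2 + 0.2 x 51.2 = 89%.

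Where the loss falls, in the middle column: at 14 days, 62 points are lost, of which the months 3-6 gap accounts for 0.2 x (92 - 14)/127 = 12. At 30 days, 11 points are lost, of which that gap accounts for 0.2 x (92 - 30)/127 = 10. So the late gap dominates only when rises last about a month or more; short rises are lost mainly between the monthly draws.

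Sensitivity: if durations vary exponentially with mean 30 days, capture is 31% in months 3-6, 63% in months 0-3, and 56% overall in the middle-column scenario. The 99% figure therefore depends on a fixed duration.

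**Step 4: effect on reading a negative result.** Let s be the share of cases detected, taken as known. With 0/40, the upper limit for true incidence is 8.8%/s: 9.8% at s = 0.9, 12.6% at 0.7 and 17.6% at 0.5. If the true rate were 17%, the upper limit would fall below 17% when 2 or fewer of 40 cases are counted. With case probability 0.17 x s, the chance of that is 2.4% at s = 1, 4.4% at 0.9, 13% at 0.7 and 33% at 0.5.

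**The case against.** **The schedule follows a stated rationale.** Draws are placed where Section 3 expects events. A reader might infer that months 3-6 repeat the fault the protocol finds in earlier trials. They do not: that criticism is about missing tests in the first two to three months, which this study samples monthly. This stands, though the early timing comes mainly from warfarin, and the protocol says that no incidence data exist for these two drugs.

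**Interim values are not excluded.** The endpoint rests on AKI being documented, and the work-up starts when AKI is noted in a participant; neither is tied to a study draw. The source-record item is also not exhaustive, since the next item takes history, medication and baseline laboratory values from the electronic record. This stands: the text is ambiguous, and it would be too strong to say that hospital-found AKI is missed by design. But the source of a primary endpoint should not be left ambiguous.

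**Short episodes are an assumption.** The protocol does not call the rise transient. A reader could take the low capture in months 3-6 as a large loss overall. That would need short rises or onsets spread over six months; with 80% of onsets early and rises of 30 to 60 days, capture is 89% to 95%.

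**The direction of bias is open.** One unconfirmed rise against a chart baseline up to three months old can also add cases. The warfarin figures come from retrospective studies whose creatinine sampling is not described, so the comparison is not shown to be tilted. Both points stand, but false positives do not make up for uncounted episodes.

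**Conclusion.** The point holds in a limited form. With four draws and no stated route for interim creatinine, the percentage is incidence detected at scheduled draws. It may understate six-month incidence. The weakest period is months 3-6, where 15% to 65% of onsets are captured for rises of 14 to 60 days. Overall capture with 80% early onset ranges from 38% at 14 days to 95% at 60 days. These figures rest on an assumed duration and onset pattern and on interim values not being counted.

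A reader might conclude that the reported incidence is biased low and that this favours the hypothesis. The protocol does not support either as a net result, because duration is unknown, onset is expected early, and the AKI definition can also inflate the count. What cannot stand as written is the assurance of detection in Section 8, and the unqualified reading of a negative result in Data Management, item ii.

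**What to change.** 1. In Human Research Methods, items vi and vii, add an extraction at month 6 of all creatinine values in the electronic record from enrolment to month 6. Count a rise of at least 0.3 mg/dL toward AKI, subject to the same exclusion of other causes, and report this incidence beside the scheduled-draw-only incidence.
2. Report incidence through month 3 separately from rises first seen at month 6. This separates the two sampling regimes but does not recover short episodes between monthly draws.
3. Reword Section 8 to say that monitoring may detect the condition. In Data Management, item ii, state that a negative result refers to cases detected by the sampling used.

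**Cost.** Protocol wording and one chart look-up for each of 40 participants, in a record the team already queries weekly for screening. No extra blood draw and no change in care. The consent and authorisation wording should be checked to confirm that it covers the look-up.

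**Downside.** Sicker patients are tested more often, so the combined figure depends on testing frequency; the scheduled-draw figure beside it makes this visible. Values measured outside this record would still be missed.

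### No follow-up item records whether the patient is still on rivaroxaban or apixaban, although the censoring rule and the objective both depend on it

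*Protocol*

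**What the plan says.** The Protocol states what will be collected in three places, and they agree.

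- **Variables** (Study Design, Human Research Methods, item vii). Drug information belongs to the baseline chart extraction: "past medical history, current medication list and baseline laboratory records (basic metabolic panel, serum creatinine, urinalysis) will be obtained from the patient's hospital chart". For follow-up the item then says: "Serum creatinine and urinalysis measurements will then be repeated at monthly intervals for the first three months and then at the six-month mark".
- **Source records** (item vi): "AECIS records for background demographic data. Laboratory results from the Einstein laboratory after serum creatinine and urinalysis are assayed". No source is named for drug continuation.
- **Study database** (item ii): "baseline data, laboratory results and work up data will be aggregated into this database using the identification numbers". The work-up data arise only in patients whose creatinine rises by the AKI threshold; the treating physician evaluates them and the team is told the result.

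Three other places depend on drug status during follow-up.

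- The objective (section 2) is the incidence of ARN in high-risk patients on these two drugs.
- An inclusion criterion reads: "Participant is willing to comply with all aspects of the protocol, including adherence to medical therapy and follow-up visit".
- Study Endpoints (item ii) and Withdrawal of Subjects (item i) both state: "Subjects will be censored from the study if anticoagulation is withdrawn for any clinical reason". Withdrawal of Subjects (item ii) adds: "If a patient is censored from the study, all of their data will be removed from the study participant list and study database".

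The primary outcome is a plain percentage, and the confidence interval is planned on a denominator of 40 (Data Management, item ii).

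**The concern.** The censoring rule needs to know, for each patient, whether the anticoagulant was withdrawn and when. No scheduled procedure supplies that. Two consequences follow.

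1. **Detection is uneven.** The one follow-up event that puts the team in contact with the treating physician is AKI. Stops are therefore most likely to be noticed in patients with AKI and least likely in patients without it.
2. **Silent stoppers count as exposed.** A patient who stops alone is not withdrawn for a clinical reason. That patient, and one whose clinical withdrawal goes unnoticed, stays in the denominator as on drug and free of ARN.

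The hypothesis is that incidence is below that reported for warfarin, and the Protocol would read a negative result as suggesting very low risk in the general population. Off-drug follow-up counted as exposed tends to favour both conclusions, and a percentage on 40 would not reveal it. No analysis plan can repair this, because it concerns what is collected.

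**Working it through.** **Step 1. The plan's own intervals.** Exact (Clopper-Pearson) 95% limits with n = 40:

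- 0/40: upper limit 1 - 0.025^(1/40) = 8.8% (Protocol: 9%)
- 2/40: 0.6% to 16.9% (Protocol: 0.6% to 17%)
- 10/40: 12.7% to 41.2% (Protocol: 13% to 41%)

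All three reproduce. They presume that all 40 patients stay in the denominator.

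**Step 2. Size of the dilution.** The Protocol gives no stopping rate, so these inputs are assumptions: a share d = 10%, 20% or 30% stops unrecorded; stop times are uniform over 0-6 months from starting the drug; there is no ARN risk after stopping. Let m be the mean share of the six-month risk that a stopper experiences before stopping. Expected cases retained = 1 - d(1 - m).

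- Even risk over time: m = 0.50.
- Front-loaded risk. The Protocol says that most cases are detected in the first eight weeks; I assume 75% in months 0-2 and 25% in months 2-6. Integrating cumulative risk over the stop time: (0.75 + 3.00 + 0.50)/6 = 4.25/6 = 0.71.

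| d | Retained, even risk | Retained, front-loaded risk |
|---|---|---|
| 10% | 0.95 | 0.97 |
| 20% | 0.90 | 0.94 |
| 30% | 0.85 | 0.91 |

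Expected cases fall by 5-15% or 3-9%, so about 3-15% overall.

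**Step 3. A second model as a check.** If all stoppers quit halfway under a constant hazard, observed incidence = (1 - d)p + d[1 - (1 - p)^0.5]. With p = 25% this gives 23.8%, 22.7% and 21.5%. In the extreme case of stoppers being off drug throughout, observed incidence = p(1 - d), or 22.5%, 20.0% and 17.5%.

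**Step 4. Comparison with precision.** At a true incidence of 10%, 40 patients give 4 expected cases. A loss of 3-15% is 0.12 to 0.60 of a case, while the exact interval for 4/40 is about 2.8% to 23.7%. At 25% the loss is 0.3 to 1.5 of 10 cases, against an interval of 13% to 41%.

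**Step 5. Why recording alone is not enough.** If 10%, 20% or 30% of stops were recorded and those patients' data deleted as written, the denominator would be 36, 32 or 28. The zero-event upper limit would rise from 8.8% to 9.7%, 10.9% or 12.3%. If deletion fell on cases, the effect would be larger. With 10 true cases among 40 and 2, 5 or 8 of them removed, the result is 8/38 = 21.1%, 5/35 = 14.3% or 2/32 = 6.3% in place of 25%. These counts are illustrative.

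**The case against.** **Withdrawals could still be learned of.** Patients remain under their primary care physician and cardiologist, cardiologists are told of the study, and the team has chart access and a weekly prescription report. A reader might infer that the censoring rule has no data behind it at all; that goes too far. What stands is that the prescription report and chart review are described for screening and baseline, and no follow-up use is specified.

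**The direction is not certain.** A reader might infer that the incidence is simply biased low. The endpoint does not require current exposure, so an unexplained creatinine rise after stopping could be counted as ARN, and no stopping rate is given. This stands: a downward shift is expected, not established.

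**The quantity is partly a choice.** The abstract speaks of the proportion developing ARN after starting a NOAC. For an incidence among initiators, stopping is part of the quantity and not an error. This stands in part. The objective and the censoring rule point to on-drug incidence, so the Protocol is mixed.

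**Alternative causes.** A reader might infer that new kidney-toxic drugs or contrast also go unrecorded. The documents do not support this. ARN is defined by a work-up that looks for other causes, its result goes to the team, and work-up data enter the database.

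**The effect is small beside sampling error.** Step 4 confirms this under the stated assumptions. It lowers the priority of the point but does not remove the mismatch between the rule and the data.

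**Conclusion.** The point holds as a gap in data collection. The Protocol fixes a list of follow-up items that contains no drug status and no stop date, while its censoring rule and objective need both. Followed as written, stops would be detected unevenly, and unnoticed stoppers would count as exposed and ARN-free. The expected effect is to lower the on-drug incidence, which favours the hypothesis. The 3-15% loss of expected cases rests on an assumed 10-30% unrecorded stopping, spread evenly over six months, with no off-drug risk. It would approach 10-30% only if every stopper quit before the first draw. The documents support neither a certain bias nor a single corrected figure.

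**What to change.** 1. **Collect drug status.** In Human Research Methods (items ii, vi and vii), add a short record at each of the four draws: which drug, still taking it (yes/no), and the date of any stop or switch. The study team takes it from the patient or the medical record. Add matching database fields.
2. **Keep the data.** Amend Withdrawal of Subjects (item ii) so that data up to the stop date are kept. Without this, better recording deletes more patients, and neither figure below can be computed.
3. **Report two figures.** Give the all-enrolled incidence with its exact binomial interval. Beside it, give an on-drug incidence: events while on drug, analysed by person-time or by time-to-event methods that censor at the stop date. A binomial interval does not suit the second figure.

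**Cost.** Patients already attend and are paid at the four draws, so no new visit or procedure is needed. The draws are done by a phlebotomist, however, and no study team member is stated to be present. A few minutes of staff time per visit or chart check must therefore be found, together with a minor amendment. No treatment changes.
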